- c) During the trial recruitment period, FIM, IAM, and AIM scales will be administered to clinical and managerial leaders from each health centre and to the staff responsible for delivering the intervention. These data will be complemented with semi-structured interviews to enhance explanatory power and to assess additional implementation criteria, including fidelity and adoption.
- d) After the 6-month assessment, clinical and managerial leaders, as well as the staff responsible for delivering the intervention, will again complete the FIM, IAM, and AIM scales, together with a complementary semi-structured interview.

Methods and procedures for the effectiveness assessment are presented in the following sections. Details on the implementation context assessment are provided later in Section 13. **IMPLEMENTATION CONTEXT ASSESSMENT**. The full set of procedures for patients is described in the effectiveness section as an integral guide to study activities, in order to avoid mistakes or confusion during data collection.

Figure 1. Study Phases Overview

Abbreviations: AIM= Acceptability of Intervention Measure; IAM= Intervention Appropriateness Measure; FIM= Feasibility Intervention Measure, Int= Intervention Dynamic DIALOG+(DD+).

v2.0-30 November 2025 BOND+ TRIAL T1_CO_PROTOCOL_Ethics_20251024_v2.0_Control_EN

Table 2. Summary of study visits procedures for patients

| Month | | | M1 | M2 | M3 | M4 | M5 | M6 | M6 | M9 | M12 | M12 | |
|---------------------------------------|---|------------|-----------|----------|-------------|--------------|---------------|--------------|-------------|---------|-----------|--------------|----------|
| Reference date for window calculation | | | Screening | Baseline | Int. I +30D | Int. II +30D | Int. III +30D | Int. IV +30D | Int. V +30D | Int. VI | 6-MA +90D | M.Int I +90D | M.Int II |
| Window (days) | | | +10 | ±10 | ±10 | ±10 | ±10 | ±10 | ±10 | ±15 | ±10 | ±10 | ±10 |
| Study visit name | | Screening* | Baseline* | Int. I | Int. II | Int. III | Int. IV | Int. V | Int VI | 6-MA | M.Int I | M.Int II | 12-MA |
| Study visit number | 0 | 1 | 2 | 3 | 4 | 5 | 6 | 7 | 8 | 9 | 10 | 11 | 12 |
| Invitation | X | | | | | | | | | | | | |
| Informed consent | | X | | | | | | | | | | | |
| MANSA QoL | | X | | | | | | | | X | | | X |
| WHOQOLBREF | | | X | | | | | | | X | | | X |
| EQ5D | | | X | | | | | | | X | | | X |
| Socio-demographics | | | X | | | | | | | | | | |
| PHQ-8 | | X | | | | | | | | X | | | X |

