- The researcher will screen participants for diabetes, obesity and HBP following standard procedures. The diagnosis will be assessed based on the in-situ screening or a previously reported and confirmed diagnosis by the healthcare provider. Screening criteria are presented in **Table 3**.
 - a. The researcher will take a capillary blood sample for assessing HbA1c levels ([Afinion™ HbA1c Abbott](#)),
 - b. Measure blood pressure with standard electronic equipment. During the visit, the assessment will be done at three moments, with at least five minutes between measurements. HBP measurement will follow the checklist and recommendations from the 2025 AHA Guideline for the Prevention, Detection, Evaluation, and Management of HBP, as well as the established study standard procedures (46).

- c. Record abdominal circumference measuring at the midway between the bottom of the ribs and the top of the hips, while the participant breathes out naturally, before taking the measurement (47).
- d. Record height and weight using validated instruments and as stated in the standard procedures.

The screening visit is finalised with the determination of the participant's eligibility. The assessment will be made by the researcher after filling out the selection criteria checklist.

Visit 2- Baseline Assessment Visit

Depending on logistical issues and the availability of the research team and participants, the screening visit and baseline assessment may be performed on the same day or a different day, considering a window of no more than ten calendar days. The baseline consists of the completion of a sociodemographic questionnaire and the remaining instruments for this visit (EQ5D, WHOQOLBREF, SIX, CSRI). The researcher will complete the baseline assessment through a patient interview. This process will take approximately 60 minutes. Visit 2 finalise with participant randomisation.

Visits 3 to 8 – Intervention visits

After randomisation, visits 3 to 8 will take place once a month (average month duration of 30 calendar days), with a 10-day window.

- Patients will be assigned to a routine clinical visit with a trial clinician. The local trial research coordinator will facilitate the appointment assignment.
- A member of the research team will accompany the patient and clinician to support them in any technical or logistical issues.
- Patient and clinician will privately go through the intervention meeting: DD+ with the solution-focused approach.

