At visit 6, a researcher will update the CSRI with participants, either at the health centre during the DD+ intervention visit or by phone within five days after the visit.

Visits 3 to 8 – Control group follow-up

Participants allocated to the control group will be followed up on monthly by phone call to assess any health events, and to remind the 6-month follow-up visit.

Visit 9- Main and secondary 6-month outcome assessment.

Within 30 days after Visit 8, a researcher will schedule Visit 9 with participants. The researcher will complete the clinical scales described in Table 1 through patient interviews. Also, HbA1c, HBP and abdominal circumference will be reassessed. For the qualitative implementation assessment, twenty-four patients will be sampled and interviewed as defined in Section 13. Semi-structured interviews will be audio-recorded and are expected to last between 30 and 60 minutes.

Visit 10 and 11- Maintenance period intervention visits

At 90 (± 10) days from visit 9 (visit 10) and 90 (± 10) days from visit 10 (visit 11), participants in the intervention arm will go through the DD+ intervention.

Visits 10 and 11 – Control group follow-up

At 90 (± 10) days from visit 9(visit 10) and 90 (± 10) days from visit 10 (visit 11), participants in the control arm will receive a follow-up phone call.

Visit 12- Main and secondary 12-month outcome assessment

At ± 10 days after visit 11, a researcher will schedule visit 12 with participants. The researcher will complete clinical scales and CSRI through patient interviews. Visit 12 will be the last study visit.

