15.11. Health Economics Analysis

15.11.1. **Measurement of health economic data**

Resource use specific to DD+ will capture both start-up (training, initial supervision, and device setup) and steady-state delivery (clinician time per DD+ session and documentation, routine/top-up supervision, app/support). These data will be obtained from site time sheets/logs and finance records in a health economics inventory form.

All other healthcare and patient-level resource use (whether under DD+ or usual care) will be collected at baseline, 6 months, and 12 months using a custom, interview-based health-economics inventory (CSRI-style) tailored to primary care for patients with co-occurring physical and mental NCDs in Colombia. Total cost per participant will be computed for 0–6 and 0–12 months from the health-system perspective.

15.11.2. **Value of resource utilization**

The amount of resource usage for each cost element will be combined with the relevant unit costs. Hourly trainer clinician wage rate will be used as the unit cost to calculate costs to training sessions and supervision, transportation expenses will be included in the implementation phase. On the other hand, hourly Health professional wage rates will be used to calculate the cost of their training, documentation and deliver DIALOG+. Unit costs for other health care services such as visits to a general practitioner, nurse, nutritionist, phycologist, social worker, psychiatrist, internal medicine or other subspecialist, and hospitalizations will be obtained from the tariff manual ISS 2001 + 30% and hospital bills (for sensibility analysis). The unit cost of the current medication prescribed to patients will be sourced from the Colombian drug price information system (SISMED in Spanish) based on the weighted price of each medication for the year. Costs will be reported in U.S. dollars (USD), using the average representative market exchange rate published by the Central Bank of Colombia (*Banco de la República*) for the study year. Sensitivity analyses will explore the impact of applying the minimum and maximum values of this exchange rate within the same year.

15.11.3. **Discounting**

No discount rate will be applied because the time horizon is 12 months.

15.11.4. **Geographical Jurisdictions**

The study will be carried out separately in 15 centers of Colombia.

15.11.5. **Measurement of effectiveness outcomes for health economic evaluation**

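### Outcome visits are dated from the preceding visit, not from randomisation, so the six- and twelve-month assessments share no common time point, and Visit 9 has two conflicting timing rules

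*Protocol*

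**What the plan says.** Randomisation closes the baseline visit (section 12.10: "Visit 2 finalise with participant randomisation"). From there Table 2 in section 10.1 has a row naming the reference date for each visit, and each entry is the visit before. For the sessions it reads "Int. I +30D | Int. II +30D | Int. III +30D | Int. IV +30D | Int. V +30D | Int. VI", and for the later visits "Int. V +30D | Int. VI | 6-MA +90D | M.Int I +90D | M.Int II". Its windows are ±10 days for each session, ±15 days for the six-month assessment, and ±10 days for both maintenance visits and the twelve-month assessment (row ending "10 | ±10 | ±15 | ±10 | ±10 | ±10").

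Section 12.10 words the primary visit differently: "Within 30 days after Visit 8, a researcher will schedule Visit 9 with participants". For the last visit it says: "At ± 10 days after visit 11, a researcher will schedule visit 12 with participants". In the control arm the same visit numbers are phone calls.

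Section 15.11.5 uses another anchor: EQ-5D-5L is to be collected at baseline and at 6 and 12 months counted from randomisation. Table 2 places EQ-5D at Visits 2, 9 and 12, so these are the same visits.

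On resource use, section 15.11.1 says that the data "will be collected at baseline, 6 months, and 12 months using a custom, interview-based health-economics inventory", and states that this covers both arms. Sections 12.6 and 12.10 (Visit 2) and Table 7 also put the CSRI at baseline. Under the heading for intervention visits, however, section 12.10 adds: "At visit 6, a researcher will update the CSRI with participants, either at the health centre during the DD+ intervention visit or by phone". The control-arm paragraph has no counterpart.

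**The concern.** The primary model in section 15.7 takes MANSA at 6 months as a single time point, adjusted for baseline. QALYs and the 0–6 and 0–12 month costs also assume fixed times. If each visit is dated from the one before, a delay at any session moves every later visit, and the six-month assessment can lie at quite different distances from randomisation. Visit 9 also has two rules that cannot both govern it. A participant who stops attending has no Visit 8 from which to date the primary assessment, yet section 15.3 keeps that participant in the intention-to-treat analysis. For the economic analysis, an extra CSRI interview in one arm only would mean that resource use is not collected in the same way in the two arms.

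**Working it through.** **The plan's own figure.** The protocol states no day range for Visit 9; its only derived figure is the sample size. SD 0.9 and correlation 0.4 give a residual SD of 0.9 × √(1 − 0.4²) = 0.825. For a difference of 0.4, 90% power and 5% two-sided, n = 2 × (0.825 × (1.960 + 1.282) / 0.4)² = 89.4, so 90 per group (power 90.2%). Then 90 / 0.8 = 112.5, so 113 per group and 226 in total. It reproduces, and visit timing does not enter it.

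**Inputs for the timing.** Day 0 is randomisation, at the end of Visit 2. Visit 3 has two readings. In Table 2 it is referenced to baseline with no days added, ±10, which gives day 0 to 10 because it cannot precede day 0. The section 12.10 text, with monthly visits after randomisation, can be read as a first session at day 30 ±10, which gives day 20 to 40. Each of the next five intervals is 30 ±10, that is 20 to 40 days.

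**Visit 8.**
- First session at baseline: 0 + 5 × 20 = 100 to 10 + 5 × 40 = 210, nominal 5 × 30 = 150.
- First session at day 30: 20 + 100 = 120 to 40 + 200 = 240, nominal 180.

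**Visit 9.** Add −15 to +15 (Table 2) or 0 to +30 (section 12.10).

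**Visit 12.** Earliest is Visit 9 + 80 + 80 − 10 = Visit 9 + 150. Latest is Visit 9 + 100 + 100 + 10 = Visit 9 + 210. Nominal under Table 2 is Visit 9 + 180.

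| First session | Visit 9 rule | Visit 9, day | Visit 12, day |
|---|---|---|---|
| Baseline | Table 2 | 85 to 225 (nominal 150) | 235 to 435 (nominal 330) |
| Baseline | Section 12.10 | 100 to 240 | 250 to 450 |
| Day 30 | Table 2 | 105 to 255 (nominal 180) | 255 to 465 (nominal 360) |
| Day 30 | Section 12.10 | 120 to 270 | 270 to 480 |

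Read literally, Table 2 puts the six-month visit at five 30-day months and the twelve-month visit at eleven.

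**Typical spread (illustration only).** Assume that each window is used uniformly and independently, with the first session on day 0 to 10. The variance of the Visit 9 date is 10²/12 + 5 × 20²/12 + 30²/12 = 250, so the SD is 15.8 days. The means are 5 + 150 + 0 = 155 (Table 2) and 5 + 150 + 15 = 170 (section 12.10). The central 95% is then about day 124 to 186, or 139 to 201: roughly two months wide, far inside the outer limits.

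**If windows did not accumulate** (each session fixed to its planned day, ±10), Visit 9 would fall on day 125 to 175 or 140 to 190 with the first session at baseline, and day 155 to 205 or 170 to 220 with it at day 30. Table 2 does not support this reading, because it names the previous session as the reference.

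**Order of visits.** Table 2's −15 days allows the primary assessment before the sixth session. The ±10 days around Visit 11 allows the twelve-month assessment before the last maintenance session. Section 12.10's Visit 9 rule does not allow the former.

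**Participants without a Visit 8.** Table 5 in section 13.3.1 reserves 6 cells × 2 = 12 of the 24 interviews, held at the six-month assessment, for patients who attended two or fewer of six sessions. The plan expects them at Visit 9 but gives no date rule for them.

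**CSRI passages side by side.** Sections 12.6, 12.10 (Visit 2) and 15.11.1 and Table 7 support a baseline collection, and section 15.11.1 and Table 7 add 6 and 12 months. Table 2, as extracted, has the first cross in the Visit 3 column, then Visits 9 and 12, and none at Visit 6. Section 12.10 alone adds a Visit 6 update, for the intervention visits only. Taken literally that is four CSRI interviews in one arm and three in the other.

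**The case against.** Section 12.10 opens by referring visit timing to Table 2, and its 30-day sentence could describe when the appointment is made, not when the visit occurs. On that reading there is one window, ±15 days. This stands as a possible reading, but the sentence should then say so, and dating from the previous visit remains either way.

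Several stronger readings are tempting, and the documents do not support them.

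- A reader might quote one range of day 85 to 240 for Visit 9. That takes its lower limit from Table 2 and its upper limit from section 12.10; no single rule gives it.
- A reader might infer that timing differs by arm because clinic sessions slip more than phone calls. The design permits this, but no figure in the protocol shows it, and the Visit 9 rule is the same for both arms.
- A reader might infer that non-completers go unassessed. Section 10.1 assesses both arms at 6 and 12 months, section 15.3 includes everyone randomised, and the interview sample relies on low attenders being present. Only the date anchor is missing.
- A reader might infer that resource use is by design measured more often with DD+. That rests on one sentence, which section 15.11.1 and Tables 2 and 7 do not carry. Any bias would also depend on the CSRI recall period, which the protocol text does not give.
- The Visit 3 position of the first CSRI cross in Table 2 may be an artefact of text extraction.
- Assessment dates are recorded (Table 7), so QALYs can be computed on actual dates. The timing problem need not carry through to them.

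**Conclusion.** The point holds as a defect of anchoring and consistency. Outcome visits are dated from the preceding visit, the windows accumulate, and this contradicts the randomisation anchor in section 15.11.5. The two Visit 9 rules are incompatible if both are visit windows. The outer limits are those in the table above; they depend on where the first session falls and on every window being used in the same direction. The narrower illustrative spread rests on an assumption of uniform, independent windows. The missing rule for a participant without a Visit 8 is a real gap. The CSRI passages contradict one another and need reconciling; they do not establish a settled difference between arms. No effect on the MANSA comparison has been quantified, and the sample size is unaffected. This should be fixed, preferably before recruitment, because the timing of assessments already made cannot be changed; it does not invalidate the design.

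**What to change.** Date Visits 9 and 12 from randomisation, at 6 and 12 months as section 15.11.5 already has it, with one stated window each. Make the rule identical in both arms and independent of how many sessions were attended or calls completed. Reconcile Table 2, section 12.10 and section 15.11.5 accordingly, and state whether the first session is counted from baseline or from 30 days later. The spacing of sessions remains the sponsor's decision.

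Give one CSRI schedule for both arms, with the baseline interview before randomisation. Check the position of the first CSRI cross in Table 2. Either drop the Visit 6 update or apply it in both arms; the control arm already has a phone call at that visit.

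The cost is wording in Table 2 and section 12.10 and a change to scheduling in REDCap. The drawback is that some participants may be assessed before a late last session, which the present Table 2 windows already allow.

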12.11. Sample Handling

Capillary blood samples will be taken from participants at the baseline visit, 6-month, and 12-month assessments. Samples will be processed immediately by a research team member at the HC and used exclusively for HbA1c estimation. Due to the collection method and the small amount of blood extracted, transport or storage of biological samples is neither possible nor expected. Biological residues will be disposed of according to each HC's procedures. If no such procedure exists, disposal will follow local regulations and will be specified in the SOP documents.

12.12. Early Discontinuation/Withdrawal of Participants

During the course of the study, a participant may choose to withdraw early from the study treatment at any time. This may happen for several reasons, including but not limited to:

- The occurrence of what the participant perceives as an intolerable Adverse Events (AE).
- Inability to comply with study procedures
- Participant decision

Any participant will be given three options when withdrawing from the study:

1. Withdrawal from active follow-up/ treatment and further communication, but allow the study team to continue to access their medical records and any relevant clinical data that is recorded as part of routine standard of care.
2. Withdrawal from active follow-up/ treatment and further communication, keeping the consent to use data already collected up to the time of withdrawal.
3. Complete withdrawal from the study, including data and samples collected up until the point of withdrawal. The data and samples already collected would not be used in the final study analysis. However, if the analysis of their data or samples has already been integrated into interim or final analysis, it should be explained to the participant.

In addition, the Investigator may discontinue a participant from the study treatment at any time if the Investigator considers it necessary for any reason, including, but not limited to:

- Ineligibility (either arising during the study or retrospectively having been overlooked at screening)
- Significant protocol deviation
- Significant non-compliance with treatment regimen or study requirements
- Clinical decision

For any of the aforementioned situations, the type of withdrawal and reason for withdrawal will be recorded in each participant's CRF.

If the participant withdraws due to an adverse event, the researcher will arrange fortnightly telephone calls until the adverse event has been resolved or the end-of-study definition is reached. Clinical management of the participant will be the responsibility of the health system the participant is affiliated with. As stated elsewhere, the security record of the intervention does not foresee AE related to the intervention or serious adverse event (SAE).

If a REC/IRB determines that it is in the best interests of the participants to terminate the study, written notification will be provided to the country's PI and CI. This may be due to, but not limited to: serious safety concerns, success or failure of the primary outcome, serious breaches, acts of fraud, critical findings or persistent non-compliance that negatively affects patient safety or data integrity. If the study is terminated, participants will be returned to their normal follow-up and routine care within the health system of each country. Other REC/IRB will be informed of the decision to determine study status in sites under their jurisdiction. PIs may pause study procedures until a final decision is taken.

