10. STUDY DESIGN

10.1. General Design

To assess the effectiveness and implementation context of DD+, we will conduct a Hybrid I Randomised Controlled Trial (RCT) using a mixed-methods approach (11,12,40). A health economic analysis will also be included to evaluate the cost of delivering the intervention in the local setting. Effectiveness will be assessed through an RCT, implementation will be evaluated through a descriptive mixed-methods implementation study, and cost-effectiveness will be assessed through an embedded health economic analysis.

Patients in selected HC (Health Centres) will be pre-screened for chronic physical and mental health conditions. Those who meet the initial criteria will be recruited. After accepting to participate and signing informed consent, they will undergo full screening for physical and mental health conditions and QoL. Patients with co-existing physical and mental NCD will be randomised to the active intervention or the control group. Healthcare practitioners (contracted research study professional/staff) trained in DD+ will deliver the assigned intervention to each active intervention participant once per month for six months. Participants allocated to the control group will continue their usual or routine care as established by the HC professionals and procedures. Participants in the control group will be contacted periodically by phone (**Figure 1**).

[figure not shown]
Participants in both study arms will be assessed for outcome measures at baseline, 6, and 12 months. **Table 2** displays the timing and content of study procedures, including interventions, assessments, and interviews across all study visits.

To assess the **implementation context**, a mixed-methods approach will be used, with the following steps:

- a) At the 6-month assessment, all patients in the intervention arm will complete the AIM and IAM scales.
- b) At the 6-month assessment, a subsample of the intervention group participants will be invited to individual interviews to enhance explanatory power and to assess additional implementation criteria, including fidelity, adoption, and feasibility.

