12.4. Informed Consent

Individuals who respond to the study information with interest will be contacted and invited by phone or letter to attend a face-to-face meeting with a researcher. Researchers will review information sheets with interested individuals and take the time to address any questions or concerns that are raised. At this stage, contact details will be confirmed and availability ascertained for attendance at intervention sessions, interviews, or appointments.

All participants will be asked to provide informed consent at the enrolment visit by signing and dating an informed consent form prior to any data collection commencing. The form will contain the exact nature of the study, what it will involve for the participant, the implications and constraints of the protocol, the

known side effects and any risks involved in taking part. It will be clearly stated that the participant is free to withdraw from the study at any time for any reason without prejudice to future care, without affecting their legal rights, and with no obligation to give the reason for withdrawal.

If signed on paper, the participant will retain one copy of the informed consent form, and the research team will keep the other, storing it in a locked filing cabinet and uploading a copy to the participant's records in the REDCap secure system (Research Electronic Data Capture). If electronically signed, the participant should receive a copy of the signed consent form on their phone or by email. If there is no available electronic source to deliver the copy, the researcher responsible for obtaining informed consent must provide a physical copy of the signed form to the participant.

All local researchers authorised to obtain informed consent will receive training based on Good Clinical Practice. Researchers must be suitably qualified with proven knowledge of current local and international clinical research regulations.

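### Section 12.12 offers a participant who wants to stop DD+ only ways to leave the study, so a literal reading loses 6- and 12-month MANSA scores that could have been collected (minor, cheap to fix)

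*Protocol*

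**What the plan says.** Protocol section 12.12 starts from treatment: "a participant may choose to withdraw early from the study treatment at any time". It then moves to the study as a whole: "Any participant will be given three options when withdrawing from the study". The three options are:

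- **Option 1** ends sessions, follow-up and contact, but leaves access to routine medical records.
- **Option 2** is "Withdrawal from active follow-up/ treatment and further communication, keeping the consent to use data already collected up to the time of withdrawal".
- **Option 3** is complete withdrawal, including data already held.

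For the investigator the wording is narrower: "the Investigator may discontinue a participant from the study treatment at any time". The listed reasons include ineligibility and non-compliance. The section does not say what happens to later assessments. It asks for the type of and reason for withdrawal to be entered in the CRF in every such case.

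Elsewhere the plan is broad. Section 10.1 says "Participants in both study arms will be assessed for outcome measures at baseline, 6, and 12 months". Section 13.3.1 samples patients who attended two sessions or fewer for interview. Section 15.3 keeps those who discontinue in their allocated group.

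Section 12.10 schedules Visit 9 from Visit 8, and Visit 12 from Visit 11. In the DD+ arm, Visits 8 and 11 are both sessions. Controls are to be "followed up on monthly by phone call to assess any health events, and to remind the 6-month follow-up visit". Table 2 marks telephone follow-up as applying to the control arm only.

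**The concern.** Stopping an intervention and leaving a trial are different decisions. Under intention to treat, the first should not cost the outcome. Section 12.12 is where a site looks when a participant says they want no more sessions, and the only forms of participant withdrawal it offers end contact. A participant willing to be interviewed at 6 and 12 months could then be recorded as withdrawn from follow-up.

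The MANSA is completed with a researcher at a study visit, so the record access under option 1 cannot replace it. Section 15.4 would impute the missing score by multiple imputation under missing at random, and the only comparison planned is with complete cases. What is at stake is avoidable missing data on the primary outcome, among people who may differ from those who complete.

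**Working it through.** **1. Sections side by side**

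| Question | 12.12 | Rest of the protocol |
|---|---|---|
| Can a participant stop DD+ alone? | Named in the opening line; no matching option | Section 2.1.1 allows the intervention to be stopped at any time |
| Are outcomes still collected? | Options 1 and 2 end follow-up and contact; option 3 also removes data | 10.1 assesses both arms at 6 and 12 months with no attendance condition |
| Are low attenders wanted in the data? | Not addressed | Table 5 reserves 6 cells × 2 = 12 of 24 interviews for them |
| Are they analysed? | Not addressed | 15.3 keeps them in their allocated group |
| When is Visit 9 for someone who stopped? | Not addressed | 12.10 counts from Visit 8, a session they would not have |

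The right-hand column shows the intention. None of it is a rule that overrides 12.12 when a participant asks to stop.

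**2. The plan's own sample size (section 15.2)**

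Inputs: SD 0.9, baseline to follow-up correlation 0.4, difference 0.4, two-sided 5%, power 90%, attrition 20%.

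- Residual variance: 0.9² × (1 − 0.4²) = 0.81 × 0.84 = 0.6804.
- n per arm = 2 × (1.960 + 1.282)² × 0.6804 / 0.4² ≈ 89.4, so 90.
- 90 / 0.8 = 112.5, so 113 per arm and 226 in total.

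The stated figures reproduce and are not in dispute. The allowance for losses of every kind is 113 − 90 = 23 per arm.

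**3. Power if further DD+ participants are lost**

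The mechanism acts on people who stop DD+, so the extra losses come from that arm only. SE = √[0.6804 × (1/n₁ + 1/n₂)] and power = Φ(0.4/SE − 1.96). The 5 and 10 extra losses are assumptions, because the protocol gives no rate of stopping.

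| DD+ n | Control n | SE | Power |
|---|---|---|---|
| 90 | 90 | 0.1230 | 0.902 |
| 85 | 90 | 0.1248 | 0.894 |
| 80 | 90 | 0.1267 | 0.884 |

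**4. Bias**

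This cannot be computed. The protocol gives neither the share who will stop nor the outcome of those who do. Section 16 expects higher losses among controls, so even the balance of missingness between arms is uncertain.

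**The case against.** The best reply is that the three options are for people leaving the study, and nothing says that stopping DD+ counts as leaving. On that reading someone who only stops sessions falls under the general schedule in 10.1, is needed for the interview matrix in 13.3.1 and stays in the analysis under 15.3. This largely stands as evidence of intention: missed sessions alone do not end follow-up, and there is no flat contradiction. It does not remove the gap, because 12.12 itself raises withdrawal from treatment and then gives that participant only study-level choices.

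Several stronger readings are tempting, but the documents do not support them:

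- **Investigator discontinuation ends outcome follow-up.** The text covers study treatment only. It is silent on follow-up, which calls for a clarifying sentence and no more.
- **People who stop DD+ have no contact.** Section 12.12 provides fortnightly calls when withdrawal is due to an adverse event. The control-arm calls exist because section 16 expects less contact there.
- **The consent form has the same fault.** Section 12.4 states the ordinary right: "the participant is free to withdraw from the study at any time for any reason without prejudice to future care". The form itself is not available, so it cannot be judged.
- **Option 3 breaks intention to treat.** Of those who choose it, 12.12 says openly "The data and samples already collected would not be used in the final study analysis". Honouring that is a necessary limit, and how it is reported is detail that can sit in the SAP.
- **The effect of DD+ will be overstated.** If 5% to 20% of the DD+ arm stopped, gained nothing, were lost and were imputed like completers, the analysis would target 0.40, while the all-randomised effect would be 0.4 × 0.95 = 0.38 down to 0.4 × 0.80 = 0.32. Both the stop rate and the zero benefit are assumptions with no basis in the protocol.

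**Conclusion.** The point holds as a minor one. Section 12.12 introduces withdrawal from treatment without giving the participant a way to do only that, and options 1 and 2 tie stopping sessions to ending follow-up and contact. Applied literally, this works against what 10.1, 13.3.1 and 15.3 intend and turns obtainable MANSA scores into missing ones.

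The power cost is small: from 0.902 to 0.894 or 0.884 for 5 or 10 extra losses in the DD+ arm, using the variance assumptions of section 15.2 and taking the control arm at 90. No size or direction of bias is claimed. The conclusion rests on sites following 12.12 as written; a site guided by the general schedule would lose nothing. It is still worth settling before recruitment, because no analysis plan can recover an outcome that was never collected.

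**What to change.** 1. Add a first option to 12.12, offered before the three existing ones: stop DD+ sessions only and continue Visits 9 and 12, with at least the MANSA completed.
2. State that when the investigator discontinues study treatment, only the sessions stop and outcome follow-up continues.
3. For participants who stop sessions, time Visits 9 and 12 at 6 and 12 months from randomisation, since their present reference points, Visits 8 and 11, are DD+ sessions in this arm.
4. Optional: give these participants the reminder calls already planned for controls.

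The cost is a few sentences in 12.12 and 12.10. The outcome visits and the call procedure already exist. The downside is modest effort to keep in touch with people who have stopped attending sessions.
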